5. SUBJECT DISPOSITION

5.1. Disposition

Subject disposition will be summarized for all screened and enrolled subjects and will include the number and percentage of subjects in the FAS, PP and safety populations, the number and percentage of subjects who have completed or discontinued the study, as well as reasons for withdrawal/ discontinuation.

Reasons for withdrawal/discontinuation will be collected on the CRF and will be summarized for subjects who withdrew/discontinued from study with the following categories:

- Adverse event
- Subject voluntarily withdrew consent
- Technical problems
- Lost to follow-up
- Investigator decision
- Death
- Other

5.2. Protocol Deviations/Violations

A deviation from the protocol is an unintended or unanticipated departure from the procedures or processes approved by the Sponsor and the independent ethics committee and agreed to by the investigator. According to the protocol, doses administered outside of specific dose requirements or defined range must be reported as protocol deviations.

All protocol deviations (significant or not) will be reviewed by the study team and sponsor prior to the database lock, to identify major protocol deviations that would potentially exclude a subject from the PP population.

A by-subject listing of protocol deviations/violations in all subjects will be provided.

6. **DEMOGRAPHICS AND BASELINE CHARACTERISTICS**

6.1. Demographics

Baseline demographics will be summarized for all subjects in the safety population. Subjects' age (years), height (cm), weight (kg), and body mass index (kg/m²) at screening will be summarized using descriptive statistics; gender, race, ethnicity, and level of education will be summarized by counts and percentages. Subject demographics will be presented in a listing.

6.2. Inclusion/Exclusion Criteria

The criteria number will be listed for screened subjects who did not satisfy the inclusion/exclusion criteria.

6.3. **Baseline Characteristics**

6.3.1. Medical History and Pregnancy Test

General medical/surgical history and neuropsychiatric history (including dementia history) will be presented in a data listing based on the safety population. A summary table by counts and percentages of medical/surgical history and neuropsychiatric history by system organ class (SOC) and preferred term (PT) will also be provided for all subjects in the safety population using version 22.0 or later of the Medical Dictionary for Regulatory Activities (MedDRA).

Pregnancy test information at the screening and imaging visits will be presented in a data listing for each female subject in the safety population. Descriptive statistics will be applied to summarize observed values for all subjects in the safety population.

6.3.2. DSM-5 Diagnostic and Neuropsychiatric Examination

Information on DSM-5 diagnostic and neuropsychiatric examinations (including Mini-Mental State Examination (MMSE), United Parkinson's Disease Rating Scale (UPDRS) Part III assessment, Hoehn and Yahr (H&Y) Scale for Parkinson's disease, and Washington Heights-Inwood Genetic Study of Essential Tremor (WHIGET) for ET) will be presented in a data listing.

6.3.3. Clinical Diagnosis

The clinical diagnosis of PS (SDD; specifically, PD, MSA, or PSP) or no SDD (ET or healthy controls) as determined by the investigator at baseline for enrolled subjects will be summarized by counts and percentages in the disposition table and will be presented in a data listing.

7. TREATMENTS AND MEDICATIONS

7.1. Prior and Concomitant Medications

Any prior and concurrent therapy or medication (and the indication for the treatment) given to a subject from 28 days prior to screening visit and throughout the follow-up period after IMP administration will be recorded in EDC. If a medication ended before IMP administration, this medication will be categorized as prior medication; if a medication started or continued to be used after the time of IMP administration, it will be categorized as concomitant medication. All medications will be mapped to PTs according to the World Health Organization (WHO) drug dictionary September 1, 2018 or later. The number and percentage of all subjects in the safety population having prior medications or concomitant medications will be tabulated by Anatomical Therapeutic Chemical Code Level 3 classification system and WHO drug PT. At each level of summarization, a subject is counted only once if she/he reported one or more medication. Prior medications and procedures, concomitant medications, and concomitant procedures will be presented in by-subject listings. If the start or end date of concomitant medications is missing, it will be imputed as shown in Section 4.4.

7.2. Thyroid Blockade

The amount and type of medication used for thyroid blockade for each subject will be summarized for all subjects in the safety population. All thyroid-blocking treatment will be included and presented in prior and concomitant medication listings.

7.3. Study Treatments

Exposure to IMP will be summarized for all subjects in the safety population. The radioactivity (in megabecquerels) of the syringe before and after injection, volume (in millilitres) of IMP administered, total radioactivity (in megabecquerels), duration of injection (seconds), and saline flush volume (in millilitres) administered will be summarized using descriptive statistics. IMP administration information recorded in EDC will be presented in a listing.

7.4. Handling of Uninterpretable Images

The image interpretation by 3 independent readers (including 10% re-read assessments) will be presented in a data listing. The image will be classified as SDD if blinded image evaluation (BIE) readers assess the image as abnormal with typical or atypical SDD, and it will be classified as no SDD if BIE readers assess the image as normal. If BIE readers determine the image is technically not adequate for interpretation or abnormal but cannot be assigned to typical and atypical SDD, the image will be defined as an uninterpretable image. The number and proportion of images that are uninterpretable will be displayed in table for all subjects by reader in FAS.

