10.2.3 Image interpretation and correlation with standard of truth

Anonymised DaTSCANTM SPECT images will be presented in randomized order to 3 independent readers. Each blinded image reviewer will determine if the image is of sufficient quality to be interpretable. If the image is not interpretable, the blinded image reviewer will be required to specify the reason why on the CRF. If the image is considered evaluable by the reader, then the reader will be required to record his/her assessment of the subject's image in terms of a normal pattern of tracer uptake (negative image interpretation) or an abnormal pattern of tracer uptake (positive image interpretation). If the image is classified as abnormal, he/she will be asked to further classify the image as typical SDD or atypical SDD.

The BIE readers will evaluate the DaTSCANTM SPECT images according to the following classification:

- 1. Normal DaTSCANTM SPECT images: 2 symmetric comma- or crescent-shaped focal regions of activity mirrored about the median plane. Striatal activity is distinct, relative to surrounding brain tissue
- 2. Abnormal DaTSCAN™ SPECT image type 1: Activity is asymmetric (i.e., activity in the region of the putamen of 1 hemisphere is absent or greatly reduced with respect to the other). Activity is still visible in the caudate nuclei of both hemispheres, resulting in a comma or crescent shape in 1 and a circular or oval focus in the other. There may be reduced activity between ≥1 striatum and surrounding tissues
- 3. Abnormal DaTSCANTM SPECT image type 2: Activity is absent in the putamen of both hemispheres and confined to the caudate nuclei. Activity is relatively symmetric and forms 2 roughly circular or oval foci. Activity of one or both is generally reduced.
- 4. Abnormal DaTSCANTM SPECT image type 3: Activity is absent in the putamen of both hemispheres and greatly reduced in one or both caudate nuclei. Activity of the striata with respect to the background is reduced.
- 5. Other: Abnormal pattern, not conforming to any of the patterns above, to be specified by the reviewer (e.g., 'punched-out' lesion such as caused by an ischaemic stroke) or if the image cannot be interpreted.

Where an image cannot be assigned to one of the categories 1) to 5) a reason must be specified in the CRF.

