12.4.4 Handling of uninterpretable images as determined by the BIE

Subjects with image(s) that cannot be interpreted from the BIE will be excluded from the primary analysis but will be included to determine the sensitivity of results.

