8. EFFICACY ANALYSIS

Efficacy analyses will be performed on both the FAS and PP populations defined in Section 4.6. Uninterpretable images will be excluded from the efficacy analysis. In cases where images are re-read, the result of the first read will be included in the efficacy analysis.

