8.1. Primary Efficacy Analysis

The sensitivity and specificity of the blinded independent read of DaTSCAN[™] SPECT images in detecting or excluding SDD, when the clinical diagnosis as established by the investigator is used as the standard of truth, will be summarized with both by-reader and majority-read analyses. Generally, True Positives (TP) include subjects with a clinical diagnosis of PS and having DatSCAN[™] assessment as SDD positive. False Negatives (FN) include subjects with a clinical diagnosis of PS but having DatSCAN[™] assessment as SDD negative. True negatives (TN) include subjects with a clinical diagnosis of ET or HV and having DatSCAN[™] assessment as SDD negative. False Positives (FP) include subjects with a clinical diagnosis of ET or HV but having DatSCAN[™] assessment as SDD positive. The efficacy will be measured by the following and presented by timepoint in the following summary tables:

- Sensitivity: Subjects with a clinical diagnosis of PS will be included. It will be defined as positive percentage agreement and calculated as the number of TP / (number of TP + number of FN): TP/(TP + FN), and a 2-sided 95% binomial confidence interval constructed around it.
- Specificity: Only subjects with a clinical diagnosis of ET will be included, which means that the HVs will be excluded from this analysis. It will be defined as negative percentage agreement and calculated as the number of TN / (number of TN + number of FP): TN/(TN + FP), and a 2-sided 95% binomial confidence interval constructed around it.
- Accuracy: Subjects with clinical diagnosis of PS, ET, and HV will be included. It will be calculated as overall percentage agreement and calculated as (TP + TN) / (TP + FN + TN + FP), and a 2-sided 95% binomial confidence interval constructed around it.

The two primary hypotheses and alternative hypotheses are:

- Sensitivity $\leq 85\%$ vs Sensitivity >0.85
- Specificity $\leq 85\%$ vs Specificity >0.85

The sensitivity will be successfully established for **a reader** if the lower bound of the 1-sided 95% confidence interval of the sensitivity for this reader is > 85%. The sensitivity will be successfully established **for the study**, only if the sensitivity is successfully established for at least two readers. The specificity will be similarly analyzed.

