Additional sensitivity and specificity analyses will be performed based on the outcome from the majority read as supportive analyses. In these analyses, only data with valid majority outcomes will be included (i.e., records with a three-way tie will not be included in this analysis.).

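### SAP 7.4 discards readable abnormal images that are not typed as typical or atypical SDD, although Protocol 10.2.3 counts them as positive; this can only raise specificity and lower sensitivity

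*SAP*

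**What the plan says.** **Protocol 10.2.3** sets an order. The reader first decides whether the image can be interpreted. If so, it is recorded as a normal pattern (negative) "or an abnormal pattern of tracer uptake (positive image interpretation"). Typing follows: "If the image is classified as abnormal, he/she will be asked to further classify the image as typical SDD or atypical SDD". Category 5 of the reader classification covers an "Abnormal pattern, not conforming to any of the patterns above, to be specified by the reviewer", but the same item also takes images that cannot be interpreted.

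**SAP 7.4** counts an image as SDD only if it is abnormal and typed as typical or atypical. It gives two routes to the uninterpretable class: the image is technically inadequate, or it is "abnormal but cannot be assigned to typical and atypical SDD, the image will be defined as an uninterpretable image".

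**SAP 8** states: "Uninterpretable images will be excluded from the efficacy analysis". **Protocol 12.4.5** has the same exclusion. **Protocol 12.4.4** adds that such subjects are "excluded from the primary analysis but will be included to determine the sensitivity of results". The SAP only tabulates and lists these images.

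**SAP 8.1** tests sensitivity and specificity per reader. A reader succeeds if the one-sided 95% lower bound exceeds 85%. The study succeeds on sensitivity "only if the sensitivity is successfully established for at least two readers", and specificity is handled in the same way. In the supportive majority read, "records with a three-way tie will not be included in this analysis".

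**SAP 11** declares no change to the protocol's statistical section.

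**The concern.** SAP 7.4 lets a secondary label decide whether a readable image enters the primary analysis. Only an abnormal read can be removed for want of a label; a normal read cannot. The exclusion therefore depends on the test result being evaluated.

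- In ET subjects, each such read is a false positive under the protocol. Removing it takes one from both FP and the denominator of TN/(TN + FP), so specificity can only rise.
- In PS subjects, each such read is a true positive. Removing it lowers TP/(TP + FN) slightly whenever there is a false negative, and it costs power.

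The majority read can change too. Three readers can produce a three-way tie only if a third outcome exists, and uninterpretable is the only one SAP 7.4 defines. An ET image read as typed abnormal, untyped abnormal and normal is a 2-to-1 false positive under the protocol. Under the SAP it appears to be a tie and drops out.

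Either primary pass/fail result can thus turn on a sub-classification that the protocol does not use to define a positive read.

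**Working it through.** **Inputs.** Threshold 0.85, assumed rate 0.95, one-sided alpha 0.05 and 60 evaluable subjects per group (Protocol 12.7, SAP 4.3); per-reader rule from SAP 8.1. Two assumptions are needed. The interval is exact (Clopper-Pearson), because the SAP says only binomial and the sizing uses an exact test. The share q of abnormal reads left untyped is varied, because the documents give none.

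**The plan's own figure.** The smallest n with exact one-sided alpha ≤ 0.05 and power ≥ 0.80 for 0.85 versus 0.95 is 59 (success at ≥ 55 correct; alpha 0.0469, power 0.828). This agrees with the plan. At n = 60 success needs ≥ 56 correct (alpha 0.0424, power 0.820).

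**Specificity, worked counts.** Protocol rule: TN/60. SAP rule with u untyped abnormal reads: TN/(60 − u). One-sided 95% lower bounds:

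| Reads | Estimate | Exact | Wilson | Wald |
|---|---|---|---|---|
| 55/60 (protocol, 5 abnormal) | 91.7% | 83.3% | 83.9% | 85.8% |
| 55/59 (SAP, 1 of 5 dropped) | 93.2% | 85.2% | 85.7% | 87.8% |
| 54/60 (protocol, 6 abnormal) | 90.0% | 81.2% | 81.8% | 83.6% |
| 54/57 (SAP, 3 of 6 dropped) | 94.7% | 87.0% | 87.5% | 89.9% |

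In the first pair one dropped read turns a fail into a pass under exact and Wilson; Wald passes both. In the second pair all three methods go from fail to pass. At the planned 95% (57/60, exact bound 87.6%) the reader passes under either rule.

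**Specificity, chance of passing when the true value is 85%.** Each of 60 ET reads is normal with probability 0.85, typed abnormal with 0.15(1 − q), or dropped with 0.15q. Let p be the chance that the exact bound exceeds 85%, summed over all counts. For at least two of three independent readers the chance is 3p²(1 − p) + p³.

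| q | One reader | At least two of three, independent |
|---|---|---|
| 0 | 4.2% | 0.5% |
| 5% | 5.5% | 0.9% |
| 10% | 6.7% | 1.3% |
| 20% | 9.4% | 2.5% |
| 33% | 16.1% | 6.9% |
| 50% | 34.2% | 27% |

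The readers see the same images, so independence is unlikely. If they always agreed, the study-level chance would equal the one-reader column.

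**Sensitivity.** With 3 true positives dropped, 57/60 = 95.0% becomes 54/57 = 94.7%. At true sensitivity 95% and 60 PS reads before exclusion, one reader's chance of passing is 82.0% at q = 0, and 68.6%, 64.5% and 50.8% when 5%, 10% and 20% of true-positive reads are untyped. Most of the first drop is a discrete step: with four misses, 55/59 has exact bound 85.2% and passes, while 54/58 has 84.9% and fails.

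**The case against.** **The protocol is itself untidy.** Category 5 combines other abnormal patterns with images that cannot be interpreted, and its example is a stroke-type lesion, which need not be SDD. SAP 7.4 could be read as resolving this, and counting every abnormal read as positive would score a vascular pattern in a PS subject as a true positive. This is a fair argument about which rule is better. It could support a declared change; it does not make a readable image uninterpretable, and the protocol's binary rule is explicit.

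**The class may be nearly empty.** Readers may use atypical SDD for anything unusual, basal ganglia infarcts of 5 mm or more are excluded at entry, and the Independent Review Charter, which is not available here, may force typing. This stands: the frequency is unknown, and shares of 33% to 50% have no support in the documents.

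**The power loss depends on the starting count.** Sixty is the planned evaluable number after a 20% loss allowance. If each reader still has 60 usable PS reads after exclusions, the chances of passing are 79.4%, 76.4% and 68.8% at 5%, 10% and 20% untyped. The loss is then smaller but does not disappear.

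**The exclusion follows the protocol.** Protocol 12.4.5 does exclude uninterpretable images, but it does not widen that class to readable abnormal ones.

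**The tie reading is inferred, and the majority read is only supportive.** Both points are correct. The per-reader primary tests are affected regardless.

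**Conclusion.** The concern holds. SAP 7.4 conflicts with Protocol 10.2.3 and the change is undeclared. The conflict is certain from the text; its effect depends on how often abnormal reads go untyped, which the documents do not say. The direction is fixed: specificity can only rise, and sensitivity cannot gain. Under an exact bound with 60 ET reads, one untyped read is enough to reverse a reader's result at 55/60. With an untyped share of 10% to 20%, one reader's false-pass chance goes from 4.2% to between 6.7% and 9.4%. For the study as a whole it stays below 5% at those shares if the readers are independent, and is higher if they tend to agree. If performance is at the planned 95%, the specificity result is not at risk. The SAP is wrong as written and should be corrected, although the practical effect may prove small.

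**What to change.** 1. In SAP 7.4, classify as SDD positive every image that the reader judges interpretable and records as abnormal, whether typed or not. Keep uninterpretable for images the reader judges not interpretable.
2. Separate other abnormal patterns from images that cannot be interpreted within category 5. If reads are already done, use the recorded interpretability judgement.
3. Apply the same rule to the majority read, and define a three-way tie.
4. Restore the Protocol 12.4.4 analysis of uninterpretable images. Add versions that count untyped abnormal reads as negative and that exclude them; these also address the stroke-type pattern.
5. If the sponsor prefers the SAP rule, amend Protocol 10.2.3 to match, give the reason, and record the change in SAP 11.

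Settle this before database lock. The cost is SAP wording and one or two tables. No new data are needed if the interpretability judgement and reasons are recorded as Protocol 10.2.3 requires. The drawbacks are that specificity may come out slightly lower, and that a non-SDD abnormality in a PS subject would count as a true positive in the primary analysis.

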7.5. Reader Difference

Subjects having DaTSCANTM assessment as SDD and no SDD will be categorized as SDD positive and negative, respectively. Intra-reader (within-reader) agreement of blinded visual image assessment will be measured by overall percentage agreement, which is calculated as the total number of subjects who have a consistent assessment on the two reads divided by the total number of all re-read subjects. This will be based on a random selection of 10% of the subjects having re-read images. An overall percentage agreement with an exact 95% confidence interval will be determined for each reader comparison and all readers for subjects with re-reads of images.

8. EFFICACY ANALYSIS

Efficacy analyses will be performed on both the FAS and PP populations defined in Section 4.6. Uninterpretable images will be excluded from the efficacy analysis. In cases where images are re-read, the result of the first read will be included in the efficacy analysis.

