12.1 General Statistical Considerations

Tabulations of summary statistics, graphical presentations, and statistical analyses will be performed with SAS® software, Version 9.2 or higher. Descriptive statistics for continuous data in summary tables will include the number of subjects in the analysis (n), mean, standard deviation, median, and range (minimum, maximum). Descriptive statistics for categorical data in summary tables will include counts and percentages. The last observation prior to administration of IMP will be used as the baseline value for calculating changes from baseline after administration of IMP. All data recorded on the CRF and entered into the database will be provided in separate data listings showing individual subject values. All summary tables and data listings will be separated by baseline diagnosis. The planning and reporting of statistical analysis will be carried out as described in the sponsor and/or CRO's SOPs governing clinical studies.

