On the basis of a previous study (DP008-003), it is projected that evaluable results will be obtained for 80% of diseased individuals and 90% of HVs. After adjustment for losses, it is therefore expected that 150 patients with movement disorders (with or without SDD) and 22 HVs will be needed to provide at least the minimum required number of evaluable subjects.

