11. CHANGES TO THE PLANNED ANALYSIS

No changes to the statistical analyses section of the protocol are made in this SAP.

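### Protocol 12.4.4 promises a robustness analysis that includes subjects with uninterpretable images, but SAP 8 carries over only the exclusion and SAP 11 declares no change

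*SAP*

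**What the plan says.** Protocol 12.4.4 states that subjects whose images cannot be interpreted in the blinded read "will be excluded from the primary analysis but will be included to determine the sensitivity of results". I read the second half as a robustness check. Protocol 12.4.5 then excludes uninterpretable images from the efficacy analysis and repeats no such exception. SAP 8 uses the same sentence as 12.4.5, directly after stating that efficacy is analysed in both FAS and PP: "Uninterpretable images will be excluded from the efficacy analysis".

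What the SAP does plan for these images is in section 7.4: a listing of all reads, and a table. "The number and proportion of images that are uninterpretable will be displayed in table for all subjects by reader in FAS". SAP 8.1 decides success by reader: the one-sided 95% lower bound must exceed 85% for at least two readers, separately for sensitivity and specificity. The majority read is supportive and drops records without a valid majority. SAP 11 states: "No changes to the statistical analyses section of the protocol are made in this SAP".

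On a related matter, SAP 7.4 says that if a read is "abnormal but cannot be assigned to typical and atypical SDD, the image will be defined as an uninterpretable image". Protocol 10.2.3 describes "an abnormal pattern of tracer uptake (positive image interpretation" in its reading instructions, while its category 5 groups other abnormal patterns with images that cannot be interpreted.

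**The concern.** Followed as written, SAP 8 drops an analysis that the protocol promises, without declaring it. Neither document says how an uninterpretable read would be scored, in which population, or at reader or majority level.

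If images are unreadable for reasons unrelated to diagnosis or to difficulty of reading, exclusion costs only sample size. If hard cases are more often unreadable, performance on readable images is better than performance in all imaged patients. The FAS cannot reveal this: it is defined without regard to evaluability, but SAP 8 removes uninterpretable images from it as well as from the PP population. Because success is decided by reader, each reader's unreadable calls shrink that reader's own denominator. No planned by-reader result then shows whether the 85% conclusion survives with those reads counted.

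**Working it through.** **Text, side by side**

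- Protocol 12.4.4: out of the primary analysis, in for a check of the results.
- Protocol 12.4.5: out of the efficacy analysis, no exception stated. If this means the primary analysis only, the two sections agree and SAP 8 omits a planned analysis. If it means all efficacy analyses, 12.4.4 has no effect. Either way a correction is needed.
- SAP 8: exclusion only, for FAS and PP.
- SAP 8.1, majority read: three readers with two outcomes cannot produce a three-way tie. The tie that the SAP mentions makes sense only if uninterpretable is a third outcome. On that reading, one unreadable and two concordant reads give a valid majority and the subject stays in. Subjects without a valid majority are dropped, and the 85% rule is not restated for the majority read.
- SAP 4.4: missing values are generally not substituted. The specific rules cover adverse events, history and medications, not reads.

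**The plan's own figure**

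Inputs (Protocol 12.7): null 0.85, alternative 0.95, one-sided alpha 0.05, power 80%. Find the smallest n for which an exact critical value r satisfies P(X ≥ r | n, 0.85) ≤ 0.05 and P(X ≥ r | n, 0.95) ≥ 0.80. Result: n = 59, r = 55, alpha 0.0469, power 0.828. The stated 59 reproduces. At the planned 60 per group, r = 56, alpha 0.042, power 0.820.

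**Illustration of what the missing analysis could show**

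Assumptions: one reader, one diagnostic group, 60 readable images, x correct, u further unreadable reads counted as non-correct. SAP 8.1 says only that the interval is binomial, so I use Clopper-Pearson: lower bound = 0.05 quantile of Beta(x, n − x + 1), with n = 60 + u.

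At the planned rate, x = 0.95 × 60 = 57:

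- u = 0: 57/60 = 95.0%, bound 87.6%, pass
- u = 1: 57/61 = 93.4%, bound 85.6%, pass
- u = 2: 57/62 = 91.9%, bound 83.8%, fail

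| Correct of 60 readable | Last pass (bound) | First fail (bound) | Unreadable reads tolerated |
|---|---|---|---|
| 56 | 56/60 (85.4%) | 56/61 (83.5%) | 0 |
| 57 | 57/61 (85.6%) | 57/62 (83.8%) | 1 |
| 58 | 58/62 (85.8%) | 58/63 (84.0%) | 2 |
| 59 | 59/63 (86.1%) | 59/64 (84.3%) | 3 |
| 60 | 60/64 (86.3%) | 60/65 (84.5%) | 4 |

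The interval method shifts this slightly. With 57 correct, Wilson also first fails at two added (57/62, bound 84.3%). Wald passes at two (86.2%) and fails at three (57/63, bound 84.4%).

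**Abnormal but unassigned reads**

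Under the positive-interpretation wording of Protocol 10.2.3, such a read is a false positive in an ET patient and a true positive in a PS patient. Under SAP 7.4 it leaves the denominator in both. The effect is favourable to specificity and unfavourable to sensitivity.

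**The case against.** The best defence is that little is hidden. Reads are listed individually, uninterpretable counts are tabulated by reader, and Protocol 12.1 adds: "All summary tables and data listings will be separated by baseline diagnosis". A version with these reads included could be worked out by hand. That stands, and it limits the severity. It does not supply the planned result or its scoring rule, which is what 12.4.4 promised.

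A second defence is that the 85% threshold was powered for evaluable subjects, so applying it to all imaged subjects changes the estimand. That also stands, and is why the bound should serve only as a reference in the added analysis.

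A reader might infer more than the documents support:

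- *That the protocol flatly contradicts itself.* Sections 12.4.4 and 12.4.5 can be read together, as shown above.
- *That no planned efficacy result includes anyone with an unreadable read.* The majority read may do so, although the general exclusion in SAP 8 leaves this unclear.
- *That any scoring rule would be chosen after the reads are known.* Nothing dates the blinded read relative to SAP approval, and the SAP is to be final before database lock.
- *That the projected loss is an uninterpretable rate.* Protocol 12.7 projects that "evaluable results will be obtained for 80% of diseased individuals and 90% of HVs", without giving causes of loss. If all of it were unreadable images and the 150 patients split equally, each group would have 0.20 × 75 = 15 unreadable. But 60/75 is capped at 80%, so missing 85% follows by construction and says nothing about the test.
- *That the scoring of unassigned abnormal reads is left open.* SAP 7.4 settles it. What remains is that it departs from the positive-interpretation wording in Protocol 10.2.3 without saying so. The Independent Review Charter, which is not among these documents, may say more.

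**Conclusion.** The point holds in this form and should be fixed. The 12.4.4 analysis is promised in the protocol, specified nowhere and dropped by SAP 8, while SAP 11 says nothing changed. The primary analysis itself is not in question.

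The possible effect is material at reader level: at the planned 95% rate, two unreadable reads counted as non-correct take a reader from 87.6% to 83.8%. This rests on the assumed 60 readable images, the exact interval and the worst-case scoring. The actual effect may be nil, since the number of uninterpretable images is not given and could be zero. The study conclusion for sensitivity or specificity changes only if fewer than two readers still pass. I am confident of the textual gap; the documents cannot say whether it would change the conclusion. The mismatch on unassigned abnormal reads is secondary.

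**What to change.** 1. Keep the primary analysis. State that the exclusion in Protocol 12.4.5 and SAP 8 applies to the primary analysis.
2. Before database lock, add to SAP 8.1 a by-reader FAS sensitivity analysis in which uninterpretable reads of PS and ET subjects stay in the denominator as non-correct. This scoring is a proposal, since 12.4.4 gives none. Show it beside the primary result with the 85% bound as a reference, labelled as a conservative supportive analysis that does not decide success.
3. If the sponsor prefers to drop the 12.4.4 analysis, declare that in SAP 11 with the reason.
4. Reconcile SAP 7.4 with Protocol 10.2.3 on abnormal but unassigned reads. This also determines which reads count as uninterpretable in step 2. In the SAP 7.4 table, show these reads separately from technically inadequate images, by diagnosis. For abnormal reads use the reader's category 5 specification; for uninterpretable images use the reason recorded on the CRF.

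Cost: one extra by-reader table, one split row and a few sentences of text; no new data. The downside is a less favourable figure beside the headline one, and the non-correct rule is harsh if images fail for purely technical reasons.
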